8.1.1.2 Consent and Collection of Specimens for Future Biomedical Research

The investigator or medically qualified designee will explain the future biomedical research consent to the participant, or the participant's legally acceptable representative, answer all of his/her questions, and obtain documented informed consent before performing any procedure related to future biomedical research. A copy of the informed consent will be given to the participant before performing any procedure related to future biomedical research.

8.1.2 Inclusion/Exclusion Criteria

All inclusion and exclusion criteria will be reviewed by the investigator, who is a qualified physician, to ensure that the participant qualifies for the study.

For Inclusion Criteria 2 and 3 (see Section 5.1 for details), a combination of medical records and/or verbal history from the participant can be used to fulfill these criteria if documented in the participant study file by the investigator.

Source documentation for all eligibility criteria needs to be maintained at the site.

For participants with $eGFR \geq 30$ mL/min/1.73 m² and < 50 mL/min/1.73 m² at Screening with stable renal function (unstable renal function is defined as a $\geq 50\%$ increase of serum creatinine compared to a value obtained at least 6 months prior to the screening visit), documentation of stable serum creatinine must be retained as source documentation at the study site.

8.1.3 Participant Identification Card

All participants will be given a participant identification card identifying them as participants in a research study. The card will contain study site contact information (including direct telephone numbers) to be used in the event of an emergency. The investigator or qualified

designee will provide the participant with a participant identification card immediately after the participant provides documented informed consent. At the time of intervention (randomization), site personnel will add the treatment/randomization number to the participant identification card.

The participant identification card also contains contact information for the emergency unblinding call center so that a healthcare provider can obtain information about study intervention in emergency situations where the investigator is not available.

8.1.4 Medical History

A medical history will be obtained by the investigator or qualified designee (refer to eCRF entry guidelines).

8.1.5 Prior and Concomitant Medications Review

8.1.5.1 Prior Medications

The investigator or qualified designee will review prior medication use at Screening/Visit 1 (see Section 6.5 and refer to eCRF entry guidelines).

8.1.5.2 Concomitant Medications

The investigator or qualified designee will record medication, if any, taken by the participant during the study.

8.1.6 Assignment of Screening Number

All consented participants will be given a unique screening number that will be used to identify the participant for all procedures that occur prior to randomization. Each participant will be assigned only 1 screening number. Screening numbers must not be re-used for different participants.

8.1.7 Assignment of Treatment/Randomization Number

All eligible participants will be randomly allocated and will receive a treatment/randomization number. The treatment/randomization number identifies the participant for all procedures occurring after treatment allocation/randomization. Once a treatment/randomization number is assigned to a participant, it can never be re-assigned to another participant.

A single participant cannot be assigned more than 1 treatment/randomization number.

8.1.8 Study Intervention Administration

The distribution of study intervention will be performed by the investigator and/or study staff at the study site visits.

At Randomization/Visit 2, study intervention will be dispensed by the study site.

Then, according to when the clinic visit is during the day, the participant will take the first dose of study intervention either in the morning or in the evening. Subsequent dosing should be performed by the participant BID approximately 12 hours apart and approximately at the same time each day for the duration of the study.

The last dose of study intervention will be on the evening prior to Visit 4. Study intervention supplies will be collected at Visit 3 and Visit 4.

8.1.8.1 Timing of Dose Administration

Study intervention will be administered orally, BID, approximately 12 hours apart for approximately 12 weeks (84 days) during the study.

A missed dose may be taken if it is <4 hours after the expected dosing time. If it is ≥ 4 hours after the expected dosing time, then the dose can be skipped, and the regular schedule resumed.

8.1.9 Discontinuation and Withdrawal

Participants who discontinue study intervention prior to completion of the intervention period should be encouraged to continue to be followed for all remaining study visits as outlined in the SoA (Section 1.3 and Section 8.10.3).

When a participant withdraws from participation in the study, all applicable activities scheduled for the Discontinuation Visit should be performed (at the time of withdrawal). Any AEs that are present at the time of withdrawal should be followed in accordance with the safety requirements outlined in Section 8.3.

8.1.9.1 Withdrawal From Future Biomedical Research

Participants may withdraw their consent for future biomedical research. Participants may withdraw consent at any time by contacting the investigator for the main study. If medical records for the main study are still available, the investigator will contact the Sponsor using the designated mailbox ([contact]). Subsequently, the participant's consent for future biomedical research will be withdrawn. A letter will be sent from the Sponsor to the investigator confirming the withdrawal. It is the responsibility of the investigator to inform the participant of completion of withdrawal. Any analyses in progress at the time of request for withdrawal or already performed prior to the request being received by the Sponsor will continue to be used as part of the overall research study data and results. No new analyses would be generated after the request is received.

In the event that the medical records for the main study are no longer available (eg, if the investigator is no longer required by regulatory authorities to retain the main study records) or the specimens have been completely anonymized, there will no longer be a link between

the participant's personal information and their specimens. In this situation, the request for specimen withdrawal cannot be processed.

8.1.10 Participant Blinding/Unblinding

STUDY INTERVENTION IDENTIFICATION INFORMATION IS TO BE UNMASKED ONLY IF NECESSARY FOR THE WELFARE OF THE PARTICIPANT. EVERY EFFORT SHOULD BE MADE NOT TO UNBLIND.

For emergency situations where the investigator or medically qualified designee (consistent with local requirements) needs to identify the intervention used by a participant and/or the dosage administered, he/she will contact the emergency unblinding call center by telephone and make a request for emergency unblinding. As requested by the investigator or medically qualified designee, the emergency unblinding call center will provide the information to him/her promptly and report unblinding to the Sponsor. Prior to contacting the emergency unblinding call center to request unblinding of a participant's intervention assignment, the investigator who is a qualified physician should make reasonable attempts to enter the intensity of the AEs observed, the relation to study intervention, the reason thereof, etc, in the medical chart. If it is not possible to record this assessment in the chart prior to the unblinding, the unblinding should not be delayed.

In the event that unblinding has occurred, the circumstances around the unblinding (eg, date, reason, and person performing the unblinding) must be documented promptly, and the Sponsor Clinical Director notified as soon as possible.

Once an emergency unblinding has taken place, the investigator, site personnel, and Sponsor personnel may be unblinded so that the appropriate follow-up medical care can be provided to the participant.

Participants whose treatment assignment has been unblinded by the investigator or medically qualified designee and/or nonstudy treating physician must be discontinued from study intervention, but should continue to be monitored in the study.

Additionally, the investigator or medically qualified designee must go into the IRT system and perform the unblind in the IRT system to update drug disposition. In the event that the emergency unblinding call center is not available for a given site in this study, the IRT system should be used for emergency unblinding in the event that this is required for participant safety.

8.1.11 Calibration of Equipment

The investigator or qualified designee has the responsibility to ensure that any device or instrument used for a clinical evaluation/test during a clinical study that provides information about inclusion/exclusion criteria and/or safety or efficacy parameters shall be suitably calibrated and/or maintained to ensure that the data obtained are reliable and/or reproducible. Documentation of equipment calibration must be retained as source documentation at the study site.

8.2 Efficacy/Immunogenicity Assessments

Compliance with the efficacy and safety assessments (along with study intervention use and visit schedule) is essential, and any noncompliance noted by the investigator or designee should result in consultation with the participant on corrective measures needed to ensure compliance.

8.2.1 Patient-Reported Outcomes

At Screening/Visit 1, each participant will be properly trained and instructed on the use of an e-Diary for completing the ePRO measures. At Screening/Visit 1, participants will be dispensed the e-Diary for completion between visits. Participants should bring their e-Diary device for all study visits and should be contacted and reminded to do so (eg, by telephone or text) before each study site visit.

Between clinic visits, participants will be instructed to complete the ePRO measures (in the following order: CSD and Cough Severity VAS) at approximately the same time each evening, as outlined in the SoA (Section 1.3). If a participant fails to complete the evening CSD and/or Cough Severity VAS ePRO measure(s), the e-Diary will allow the participant, based on recall, to complete these missed measures in the next day (also see vendor's site manual for further details). Participants will be prompted within the e-Diary to complete the missed measures first, prior to the measures for the current day.

At the clinic visits, participants will be asked to complete ePRO measures (in the following order: Cough Severity VAS, LCQ, PGIC, and WPAI), as outlined in the SoA (also see vendor's site manual for further details). All Visit 2 ePRO measures MUST be activated and completed prior to the first dose of study intervention/randomization (see vendor's site manual for further details). For subsequent clinic visits, the e-Diary must be activated by the site to enable the collection of the ePROs at the clinic visit.

Electronic PRO measures must be activated, as outlined in the SoA (Section 1.3). More details on PRO measures are given in Section 4.2.1.1.

Participants who discontinue study intervention early will continue to be monitored in the study and should be encouraged to continue to complete the ePRO measures for the remaining visits (as outlined in the SoA, Section 1.3) through the end of the study.

Compliance with daily completion of the eDiaries must be monitored by the investigator or designee. Each investigator site will contact individual participants who are non-compliant in order to retrain and/or remind them to complete their assessments as per the SoA (Section 1.3). Discussion with the participant and retraining will be performed if any question on any e-Diary is missing and/or if any e-Diary scheduled for completion per the SoA is missing, in error.

Once a participant has completed the study (or discontinued from the study), the participant should return the e-Diary to the study site, and all ePRO measures should be deactivated.

Data collection for all ePRO measures will be dependent on ePRO device and software availability.

8.2.1.1 Leicester Cough Questionnaire

Participants will be asked to complete the 19-item LCQ to assess the impact of their cough severity on physical, social and psychological functioning, as detailed in SoA (Section 1.3).

Leicester Cough Questionnaire will be completed at Randomization/Visit 2, after eligibility for randomization has been confirmed, and at Visits 3 and 4 before all other assessments.

8.2.1.2 Cough Severity Diary

Participants will complete the CSD at approximately the same time each evening before going to bed beginning at Visit 1 and continuing through Visit 4, as outlined in the SoA (Section 1.3).

8.2.1.3 Cough Severity Visual Analog Scale

Participants will be asked to rate the severity of their cough over the past 24 hours using a 100-mm Cough Severity VAS single-item questionnaire, with the response ranging from 0 (“No Cough”) to 100 (“Extremely Severe Cough”).

At Screening/Visit 1, participants will complete a single Cough Severity VAS questionnaire at the study visit in order to assess the eligibility criterion. For the remainder of the study, beginning with the evening of Screening/Visit 1, participants will complete the Cough Severity VAS at approximately the same time each evening before going to bed, as outlined in the SoA (Section 1.3). The Cough Severity VAS assessment completed the evening before Randomization/Visit 2 will be used as the baseline value and to assess the Randomization/Visit 2 Cough Severity VAS eligibility criterion. If the assessment was not completed the evening before randomization, then a measurement done on the day of randomization, prior to any non-PRO Randomization/Visit 2 procedures, can be used as the baseline value and to assess the Randomization/Visit 2 Cough Severity VAS eligibility criterion.

In order to confirm participant eligibility, study site staff will be required to review/confirm the participant met the Cough Severity VAS eligibility criteria from the measurement done at Screening/Visit 1 at the clinic and the measurement done the evening before Randomization/Visit 2 (or from the morning of Randomization/Visit 2, prior to conducting any Visit 2 procedures, if the evening measurement was missed). A score of ≥ 40 mm on the Cough Severity VAS, for both Screening/Visit 1 and Randomization/Visit 2 is required for randomization into the study.

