9 STATISTICAL ANALYSIS PLAN

This section outlines the statistical analysis strategy and procedures for the study. If, after the study has begun, but prior to any unblinding, changes are made to primary and/or key secondary hypotheses, or the statistical methods related to those hypotheses, then the protocol will be amended (consistent with ICH Guidance E9). Changes to exploratory or other non-confirmatory analyses made after the protocol has been finalized, but prior to unblinding, will be documented in a sSAP and referenced in the CSR for the study. Post-hoc exploratory analyses will be clearly identified in the CSR.

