9.10 Subgroup Analyses

Analysis for the primary efficacy endpoint will be provided for the following subgroups of baseline factors:

- Gender (male, female)
- Region (North America, Europe, Asia-Pacific, Other)
- Age group (<60 years, ≥ 60 years old)
- Baseline Cough Severity VAS (<60 mm, ≥ 60 mm)
- Potential co-morbid conditions associated with cough (ie, GERD, asthma, UACS)
Note: Details of the conditions will be provided in a separate sSAP.
- Concomitant medications (ie, antitussives and treatments for potential co-morbid conditions, proton pump inhibitors, inhaled corticosteroids first-generation anti-histamines). Note: Details of the concomitant medications will be provided in a separate sSAP.

A similar longitudinal ANCOVA model as that used for the primary efficacy endpoint will be utilized. For each subgroup, summary statistics including means and their 95% CIs will be provided for each intervention group at Week 12. For the subgroups with 15% or more of the FAS population across both intervention groups, the mean treatment differences (gefapixant - placebo) and their 95% CIs will also be provided at Week 12.

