1. INTRODUCTION

This supplemental SAP (sSAP) is a companion document to the protocol. In addition to the information presented in the protocol SAP which provides the principal features of confirmatory analyses for this trial, this supplemental SAP provides additional statistical analysis details/data derivations and documents modifications or additions to the analysis plan that are not “principal” in nature and result from information that was not available at the time of protocol finalization.

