3.4.3 Derivations of Efficacy Endpoints

Baseline for efficacy variables is defined as the last non-missing value prior to the first study treatment.

Data Handling Rules for Efficacy Endpoints

- **LCQ Total Score**

There are three domains in the LCQ instrument: Physical (items 1, 2, 3, 9, 10, 11, 14 and 15), Psychological (items 4, 5, 6, 12, 13, 16, and 17), and Social (items 7, 8, 18, and 19). For each domain, the domain score (range 1-7) is the sum of individual item score within the domain divided by the number of items in the domain. The LCQ total score (range 3-21) is the sum of the three domain scores.

The Physical domain score will be considered as missing if more than 2 items are missing. If there is only 1 missing item, the Physical domain score will be based on the actual non-missing items. Psychological domain score will be derived in a similar fashion. Social domain score will be considered as missing if any item is missing. The LCQ total score will be considered as missing if any of the 3 domain scores is missing.

- **Cough Severity VAS score**

Cough severity VAS is scored from 0 to 100 using a 100 mm visual analogue scale. Mean weekly VAS score will be derived as the average of the VAS scores collected during the week prior to each visit. Baseline is defined as the average of VAS scores collected during the week prior to Day 1 (Day -7 to Day -1).

The mean weekly VAS score will be considered as missing if there are more than 3 missing days during the week prior to each visit. If there are less than 7 but at least 4 non-missing days during the week prior to a visit, the mean weekly score will be based on the actual non-missing days of the week prior to the visit.

- **CSD Total Score**

The daily CSD instrument has a total of 7 items, each with scores ranging from 0 (best) to 10 (worst). The total daily CSD score is the sum of these seven item scores. Mean total daily score (the sum of 7 item scores divided by 7) and three subscales (cough frequency, intensity, and disruption) will be derived for each day. Mean weekly total score is defined as the average of the mean total daily scores collected during the week prior to each visit. Mean weekly subscales will be derived in a similar fashion. Baseline is defined as the average CSD scores collected during the week prior to Day 1 (Day -7 to Day -1).

[figure not shown]

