3.5 ANALYSIS POPULATIONS

3.5.1 Efficacy Analysis Populations

The FAS population will serve as the primary population for the analysis of efficacy data in this study. The FAS population consists of all randomized participants who have taken at least 1 dose of study intervention. For endpoints that are measures of change from baseline, participants need to have baseline and at least one post-baseline measurement for inclusion in the analysis of each specific endpoint. Per-Protocol (PP) population excludes participants due to important violations from the protocol that may substantially affect the results of the primary efficacy endpoint. Potential violations that may result in the exclusion of a participant from the PP population will be specified in this document approaching database lock. The final determination on important protocol violations, and thereby the composition of the PP population, will be made prior to the first unblinding of the database and will be documented in a separate memo. A supportive analysis using the PP population may be performed for the primary efficacy endpoint if the proportion of the participants with important protocol deviations is >10%.

The list below shows important protocol violation criteria that may be considered as affecting the results of the efficacy endpoints:

Participants will be included in the intervention group to which they are randomized for the analysis of efficacy data using the FAS population. Details on the approach to handling missing data are provided in Section 3.6 – Statistical Methods.

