A participant will be considered for inclusion in the assessment of an efficacy endpoint if the CSD and Cough Severity VAS are completed on at least 4 days during the 7-day period prior to a post-Baseline visit (other ePROs are completed at the clinic visit only). All efficacy analyses will be conducted based on the observed data only. No imputation is planned for the missing diaries or missing questionnaire items. The pattern of missing is assumed to be missing at random (MAR). The missing pattern will be inspected to determine if the MAR assumption is met. Sensitivity analyses will be implemented to explore the impact of departures from the assumption made in missing diaries.

The longitudinal ANCOVA model (aka. LDA method) assumes that data are missing at random. In this study, it is expected that missing at random and missing completely at random (MAR/MCAR) mechanisms will underlie most of the missingness, and the proportion of data missing not at random (MNAR), driven solely by unobserved values of the study endpoints, will be small.

In addition to the analysis approach specified in the above mentioned primary efficacy endpoint analysis section, the following sensitivity analyses will be used to assess the robustness of the primary analysis approach.

Tipping-point Multiple-imputation Analysis

The Variant 3 of the tipping point as described in paper [Ratitch et al. 2013] will be used. In that approach, missing data are first imputed for all visits under the MAR assumption, and then the worsening/shift is applied. This is repeated with increasing the delta-shift (worsening) until the result is no longer statistically significant. Specifically, for a given constant, c , the tipping point analysis is conducted in a fashion similar to that used in standard multiple imputation, whereby m ($=100$) complete datasets are randomly generated using the original observed dataset. These m complete datasets are subsequently analyzed using the primary model, and the results of those analyses are then combined. The construction and analysis of these m ($=100$) datasets requires four primary steps:

- 1) Using a Markov Chain Monte Carlo method, make the observed dataset monotone-missing. This will be accomplished for each treatment group using “proc mi” within SAS 9.3 or higher by utilizing the options “mcmc chain=multiple impute=monotone;”, in conjunction with all of the covariates (excluding treatment)

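### Does the trial have two conflicting VAS baselines and an unusable CSD score definition?

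*Combined protocol and SAP*

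**What the plan says.** **VAS baseline.** Protocol 8.2.1.3 states: "The Cough Severity VAS assessment completed the evening before Randomization/Visit 2 will be used as the baseline value". The same reading serves the Visit 2 eligibility check (at least 40 mm), and a Day 1 reading may stand in if the evening entry was missed. The sSAP, 3.4.3, opens with a general rule for efficacy variables, the last value available before first treatment. It then gives VAS its own rule: "Baseline is defined as the average of VAS scores collected during the week prior to Day 1", that is, Day -7 to Day -1. Follow-up VAS is a mean over the week before each visit.

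**Which document governs.** Protocol Section 9 says: "Changes to exploratory or other non-confirmatory analyses made after the protocol has been finalized, but prior to unblinding, will be documented in a sSAP". The sSAP introduction says that "this supplemental SAP provides additional statistical analysis details/data derivations".

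**Diary days.** The sSAP, 3.4.3, treats the weekly VAS mean as "considered as missing if there are more than 3 missing days during the week prior to each visit". Section 3.6.1 words its inclusion rule as diaries "completed on at least 4 days during the 7-day period prior to a post-Baseline visit". For change endpoints, section 3.5.1 adds that "participants need to have baseline and at least one post-baseline measurement for inclusion in the analysis of each specific endpoint".

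**CSD.** Protocol 4.2.1.1 describes seven items scored 0 to 10 in three domains (3, 2 and 2 items). It gives domain averages a range of 1 to 7 and their sum a range of 3 to 21. The sSAP, 3.4.3, defines the daily total as the sum of the seven items, also derives the seven-item mean, and builds the weekly total on that mean. Section 3.6.1 names the weekly average of the daily total as the analysed quantity.

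**The concern.** Two definitions of one baseline in a protocol and its companion SAP are normally worth correcting. VAS is the only secondary efficacy endpoint, its baseline is a covariate in the model, and baseline VAS splits participants at 60 mm for a subgroup analysis of the primary endpoint. The Day 1 fallback lies outside the Day -7 to Day -1 window, so the two rules can give different values for the same participant.

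The single reading is noisier than a seven-day mean and is also the entry score. Used as the analysis baseline, it would bring more regression to the mean into the within-arm change, explain less of the follow-up variance, and place some participants on the other side of the 60 mm cut. If the minimum number of diary days did not apply to the baseline week, it would be unclear who has a VAS baseline at all. The CSD ranges are arithmetically impossible, and with the sSAP's sum and mean three scales are in play.

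**Working it through.** **1. Which VAS rule applies.**
- Protocol Section 3 attaches a hypothesis to the LCQ only, and the multiplicity summary in 9.1 counts one hypothesis. VAS is therefore non-confirmatory, and so is a descriptive subgroup table.
- For such analyses, Section 9 names the sSAP as the place where changes are recorded.
- Within the sSAP, the general last-value rule is followed by a VAS-specific rule, and the specific one governs. It directly follows the definition of the weekly follow-up mean.
- The sSAP change log of 13JAN2021 records an update to the week used for the diary baselines, so the weekly baseline was deliberate.
- The protocol defines no weekly-mean VAS for follow-up. An analyst who takes that rule from the sSAP meets the matching baseline rule in the next sentence.

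Sites use the evening reading for eligibility; the analysis uses the weekly mean. No new data are needed: diaries start on the evening of Visit 1, and Visit 2 is at least 7 days later (protocol 8.10.2).

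**2. What the wrong choice would do.** The documents give no VAS variances, so these are assumptions: mean 60 to 70 mm; between-person SD 15 or 18; day-to-day SD 5, 10 or 15, independent across days; at least 40 mm required at screening and on the last evening.

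| Quantity | Single evening | Weekly mean |
|---|---|---|
| Regression to the mean within an arm | 0.1 to 2.6 mm | 0.0 to 0.4 mm |

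The two definitions put 7 to 26% of participants on different sides of 60 mm.

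The loss of precision is the square root of (1 - r²) for the single reading divided by (1 - r²) for the weekly mean, where r is the correlation of each baseline with the follow-up week. It depends on how strongly a person's true level at baseline and at Week 12 correlate:

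| Assumed correlation | Increase in standard error with the single evening |
|---|---|
| 0.3 | about 0.3 to 1.5% |
| 0.6 | 1.6 to 7.3% |
| 0.9 | 11 to 29% |

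The documents do not say which row applies. Either baseline is measured before the first dose and defined alike in both arms, so regression to the mean cancels in the between-arm contrast, which stays unbiased.

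**3. Baseline diary days.** The missing-days rule in 3.4.3 refers to each visit. Visit 2 is a visit, and Day -7 to Day -1 is the week before it. Section 3.6.1 concerns post-baseline assessments and does not exempt baseline. Section 3.5.1 already gives the consequence of a missing baseline, and a model with baseline as a covariate drops such participants anyway.

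The number affected is 414 × P(fewer than 4 of 7 entries), assuming independent misses:

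| Daily completion | Probability | Participants of 414 |
|---|---|---|
| 80% | 0.0333 | 13.8 |
| 85% | 0.0121 | 5.0 |
| 90% | 0.0027 | 1.1 |
| 95% | 0.0002 | 0.1 |

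**4. CSD ranges.**
- Items 0 to 10: each domain average runs 0 to 10, and the sum of three domains runs 3 × 0 = 0 to 3 × 10 = 30. The stated 1 to 7 and 3 to 21 do not reproduce.
- Items 1 to 7: the domain runs 1 to 7 and the sum 3 to 21. These are the LCQ figures given earlier in the same protocol section, so the slip looks like a carry-over.
- The sSAP sum runs 0 to 70 and the sSAP mean 0 to 10. One is the other divided by 7, so estimate and standard error scale together and the p-value is identical.
- The protocol's sum of domains is not a rescaling: frequency has weight 1/3 there and 3/7 in the sSAP. A 2-point gain on the three frequency items is 2/30 = 6.7% of the range, against (6/7)/10 = 8.6%.

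Protocol 9.6.1 leaves exploratory methods to the sSAP, so the protocol's sum of domains describes the instrument and is not the analysed score.

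**The case for a change.** The strongest argument for acting is that the order of precedence has to be inferred. The protocol assigns the evening reading two uses, baseline and eligibility, so it cannot be read as eligibility wording alone. The sSAP change log mentions only the length of the week, not a departure from the protocol. The general last-value rule in sSAP 3.4.3, read literally for VAS, gives a single score. Section 3.3 of the sSAP even speaks of secondary hypotheses. The subgroup split could move a quarter of participants, and the repair is a few words.

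Much of this is factually right. No text says outright that the weekly mean replaces the evening reading, and a cross-reference would be tidier. The inference is nevertheless short: the protocol states no secondary hypothesis for section 3.3 to point to, and a specific rule follows the general one. The subgroup figure compares the two definitions; it becomes an error only if the analyst sets aside the rule in the analysis document. The CSD sum-or-mean ambiguity in the sSAP is real but affects only the reporting unit, which any table must label.

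**Conclusion.** No change to the plan follows. The VAS discrepancy is a missing cross-reference on a non-confirmatory endpoint, and the sSAP's specific rule settles it sensibly. The CSD ranges are a clerical slip in a description of the instrument. The minimum number of baseline diary days is largely covered by the sSAP's own wording, and would affect about 0 to 14 of 414 participants at 95 to 80% daily completion. The primary LCQ test, alpha, the sample size and the unbiasedness of the VAS contrast are unaffected.

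This rests on reading the sSAP as governing VAS and subgroup derivations, which the protocol supports in general terms but not item by item. The VAS figures rest on assumed variances and correlations, and the conclusion does not depend on them. The wording could be tidied whenever the documents are next revised, but no result waits on it.
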